#### **Part A, Cohort A3: Effect of Milk**

In addition to the above instructions for dosing under fed conditions, on Day 9 (open-label VX-121 suspension, fed state and with milk), administration of the VX-121 suspension will be followed by a glass of skim milk (240 mL). Water will be consumed with dosing as needed to rinse suspension from the dosing vial. Refer to the FPI for additional information.

#### **Part A, Cohort A9: Relative Bioavailability and Effect of Milk**

On the Day 1, 9, and 17 Visits (fed state), subjects must abstain from all food and drink (except water) at least 8 hours before the start of the standard breakfast. A standard breakfast, containing approximately 20 g of fat, will be served to subjects 30 minutes before dosing. Subjects must complete the entire meal in 30 minutes or less; study drug will be administered 30 minutes after the start of the meal. Food will not be permitted for at least 4 hours after dosing. Water (including clear liquids) may be consumed without restriction beginning 1 hour after dosing. On Day 17 (tablet, fed state and with milk), administration of the VX-121 tablet will occur with a glass of skim milk (240 mL) instead of water.

Lunch will be provided approximately 4 to 5 hours after dosing. Dinner will be provided approximately 9 to 10 hours after dosing.

An evening snack will be permitted.

#### **Part B**

All cohorts in Part B will be dosed under fed conditions.

On all days of study drug administration, a standard breakfast (containing approximately 20 g of fat) will be served 30 minutes before morning dosing. Subjects must complete the entire meal in 30 minutes or less; study drug will be administered 30 minutes after the start of the meal.

On days of intensive PK sampling, subjects must abstain from all food and drink (except water) at least 8 hours before the start of the standard breakfast. Food will not be permitted for at least 4 hours after the morning dose but water and other clear liquids may be consumed without restriction beginning 1 hour after the morning dose.

#### **Part C**

All doses of VX-121, TEZ, and IVA will be administered under fed conditions, consistent with the dosing recommendations for TEZ/IVA.

Subjects will be given a standardized meal (standard breakfast containing approximately 20 g of fat; standard dinner containing approximately 30 to 60 g of fat) 30 minutes (for breakfast) or

45 minutes (for dinner) before all doses of study drug on the Day 1 to 14 Visits. Subjects must complete the meal within 30 minutes (for breakfast) or 45 minutes (for dinner); study drug will be administered 30 minutes (for breakfast) or 45 minutes (for dinner) after the start of the meal.

On days of intensive PK sampling, subjects must abstain from all food and drink (except water) at least 8 hours before the start of the standard breakfast. Food will not be permitted for at least 4 hours after the morning doses but water and clear liquids may be consumed without restriction beginning 1 hour after the morning dose.

### **9.6.2            Part D**

Study drug will be administered orally. Subjects will receive the same number of tablets each day to maintain the blind. Additional information is provided in the Pharmacy Manual. Food restrictions, including potential dairy restrictions, will be specified in the Study Reference Manual.

Study drug will be administered with a fat-containing meal or snack, such as a standard CF high-fat, high-calorie meal or snack or a standard meal, according to the following guidelines:

1. It is recommended that the dose be taken within 30 minutes after the start of the meal or snack.
2. Study drug or placebo will be administered q12h or qd ( $\pm$  2 hours). VX-121 and TEZ will be administered qd and IVA will be administered q12h. For each subject, all doses of study drugs will be taken at approximately the same time each day. For example, the morning dose could be taken at 08:00 every morning and the evening dose could be taken at 20:00 every evening throughout the study.
3. The date, amount taken, and time of study drug administration, including whether food was taken with each dose, will be recorded for the 2 doses before PK sample collection and the dose received on the morning of PK sample collection.
4. On days of scheduled visits, the morning dose of study drug will be administered at the site after predose assessments have been completed. The meal or snack will be provided by the site for the morning dose of study drug.
5. If a subject's scheduled visit is to occur in the afternoon, the following guidelines must be used:
  - If the dose in the clinic will be within 6 hours of the subject's scheduled morning dose, the subject should withhold the morning dose of study drug and the morning dose will be administered in the clinic.
  - If the dose in the clinic will be more than 6 hours after the subject's scheduled morning dose, the subject should take the morning dose at home.
6. For visits after the Day 1 Visit, subjects will be instructed to bring all used and unused study drug to the site; study drug will be dispensed at each visit, as appropriate.

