**Table 3-7 Study VX17-121-001: Part D, Screening, Treatment Period, and Safety Follow-up Visit**

Event/Assessment a	Screening Visit b	Treatment Period c				ETT Visit d	Safety Follow-up 28 (± 7) Days After Last Dose of Study Drug
	Days -28 to -1	Day 1	Day 8 (± 1 day)	Day 15 (± 1 day)	Day 29 (± 1 day)		
Outpatient visits	X	X	X	X	X	X	X
Informed consent	X						
Randomization e		X					
Demographics	X						
Medical history	X						
Weight f	X	X	X	X	X	X	X
Height f	X						
Vital signs g	X	X	X	X	X	X	X
Pulse oximetry g	X	X	X	X	X	X	X
Physical examination h	Complete	Abbreviated	Abbreviated	Abbreviated	Abbreviated	Abbreviated	Complete
Standard 12-lead ECG i	X	X	X	X	X	X	X
Sweat chloride j,k	X	X	X	X	X	X	X
Spirometry l	X	X	X	X	X	X	X
Urinalysis j	X	X	X	X	X	X	X
Serum β-hCG (all female subjects)	X						

a All assessments will be performed before dosing, unless noted otherwise. Assessments that are collected before and after dosing will only be collected once if study drug is not administered on the day of the visit (i.e., premature discontinuation of study drug treatment).

b All screening results must be reviewed before randomization, unless noted otherwise.

c To qualify to continue into the Treatment Period, conditions for entry must be satisfied ([Section 9.1.2.2](#)).

d If the subject prematurely discontinues study drug, an ETT Visit should be scheduled as soon as possible after the decision to terminate study drug treatment. Additional PK samples and safety assessments may also be performed at the discretion of the investigator. See [Section 9.1.2.4](#) for additional details.

e Randomization may occur on the previous day (Day -1) after all conditions for entering the Treatment Period have been confirmed ([Section 9.1.2.2](#)).

f Weight and height will be measured with shoes off.

g Vital signs and pulse oximetry will be collected after the subject has been at rest for at least 5 minutes.

h Complete and abbreviated PEs are described in [Section 11.7.3](#).

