i Standard 12-lead ECGs will be performed in the supine position after the subject has been at rest for at least 5 minutes. The ECG will be done before any other procedures that may affect heart rate, such as blood draws. On Days 1 and 15, ECGs will be collected before dosing and 4 hours (± 1 hour) after dosing. ECGs collected on Day 1 before dosing will be performed in triplicate.

j The predose assessment on Day 1 may be performed on the previous day (Day -1) if randomization has occurred.

k Sweat chloride will be measured in all subjects. See [Section 8.2.1](#) for information about the sweat chloride assessment for study eligibility.

l Spirometry may be performed pre- or post-bronchodilator at the Screening Visit. Spirometry will be performed pre-bronchodilator, before the morning dose of study drugs, and should be performed at approximately the same time at every other study visit. On Days 1 and 15, spirometry will also be performed pre-bronchodilator 5 hours (± 1 hour) after study drug administration.

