**Table 3-7 Study VX17-121-001: Part D, Screening, Treatment Period, and Safety Follow-up Visit**

Event/Assessment a	Screening Visit b	Treatment Period c				ETT Visit d	Safety Follow-up 28 ( $\pm$ 7) Days After Last Dose of Study Drug				
	Days -28 to -1	Day 1	Day 8 ( $\pm$ 1 day)	Day 15 ( $\pm$ 1 day)	Day 29 ( $\pm$ 1 day)						
CFTR genotype m	X										
FSH n	X										
Serum chemistry and hematology j	X	X	X	X	X	X	X				
Coagulation j	X	X	X	X	X		X				
PK sampling p		X	X	X	X	X					
Randomized study drug dosing q		Day 1 through Day 29									
Adverse events	Continuous from signing of ICF through Safety Follow-up Visit										
Medications review r	Continuous from signing of ICF through Safety Follow-up Visit										
Treatment and procedures review	Continuous from signing of ICF through Safety Follow-up Visit										

m CFTR genotyping will be performed for all subjects. If the screening CFTR genotype result is not received before randomization, a previous CFTR genotype laboratory report may be used to establish eligibility.

n FSH will be measured for any suspected postmenopausal female subjects with at least 12 months of continuous spontaneous amenorrhea.

p Blood samples will be collected for PK analysis of VX-121, TEZ and metabolites, and IVA and metabolites. On Day 1, samples will be collected before dosing (0 hours) and at 1, 2, 4, and 6 hours after dosing (relative to the morning dose). On Days 8 and 29, a predose sample will be collected before the morning dose of study drug (0 hours). On Day 15, samples will be collected before dosing (0 hours) and at 1, 2, 4, 6, and 8 hours after dosing. Acceptable PK sampling windows are provided in Table 11-1. At the ETT Visit, a single blood sample for PK analysis will be collected.

q The last dose of study drug will be the morning dose on the Day 29 Visit.

r All medications taken from 28 days before the Screening Period through the end of the study will be recorded.

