### **11.7.5 Spirometry (Part D Only)**

Spirometry will be performed according to the American Thoracic Society Guidelines/European Respiratory Society Guidelines.

Spirometry will be performed as outlined below:

Pre-bronchodilator spirometry is defined as spirometry testing performed for subjects who have

- withheld their short-acting bronchodilators (e.g., albuterol) or anticholinergic (e.g., ipratropium bromide [Atrovent®]) for more than 4 hours before the spirometry assessment;
- withheld their long-acting bronchodilator (e.g., salmeterol) for more than 12 hours before the spirometry assessment; and
- withheld their once-daily, long-acting bronchodilator (e.g., tiotropium bromide [Spiriva®]) for more than 24 hours before the spirometry assessment.

During the Screening Period, spirometry assessments may be performed pre- or post-bronchodilator. At all other visits, all spirometry assessments should be performed “pre-bronchodilator.” During the Treatment Period, spirometry assessments must be performed before the morning dose of study drugs at approximately the same time at each visit. Postdose spirometry assessments will be performed as noted in [Table 3-7](#).

In the event that a subject forgets to withhold bronchodilator(s), spirometry should be performed according to the following:

- If a subject’s Day 1 Visit spirometry assessment is pre-bronchodilator but, on a subsequent visit, the subject forgets to withhold bronchodilator use, a post-bronchodilator spirometry assessment will be obtained for that visit only, and the visit will not be rescheduled.
- If, on the Day 1 Visit, the subject forgets to withhold his/her dose of bronchodilator, spirometry should be performed post-bronchodilator, and all subsequent spirometric measurements (according to the schedule of assessments detailed in [Table 3-7](#)) should be performed post-bronchodilator.
- Each spirometry assessment will be recorded in the source documents as pre- or post-bronchodilator.

If more than 1 spirometry assessment is required at a visit, bronchodilators will be withheld until completion of the last scheduled spirometry assessment.

All sites will be provided with spiroometers to be used for all study assessments. Spirometry data will be transmitted to a centralized spirometry service for quality review.

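### Part D: the home-dosing rule for late afternoon visits makes predose spirometry and the 0 h PK sample unobtainable at an affected Day 8, 15 or 29 visit, and SAP Appendix A does not clearly select the predose Day 15 test

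*Protocol*

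**What the plan says.** Protocol 9.6.2 item 4 places the visit-day morning dose at the site, after the predose assessments. Item 5 then deals with late visits: if a subject's "scheduled visit is to occur in the afternoon, the following guidelines must be used". A clinic dose that would fall within 6 hours of the usual time is withheld and given at the visit. Beyond 6 hours after the "scheduled morning dose, the subject should take the morning dose at home". Neither branch names or exempts particular visits.

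On spirometry, Protocol 11.7.5 says that in the Treatment Period "spirometry assessments must be performed before the morning dose of study drugs at approximately the same time at each visit". Table 3-7 footnote l repeats the predose requirement and says that testing "should be performed at approximately the same time at every other study visit". It adds a postdose test: "On Days 1 and 15, spirometry will also be performed pre-bronchodilator 5 hours (± 1 hour) after study drug administration".

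On PK, Table 3-7 footnote p asks for a 0 h sample before the morning dose on Days 8, 15 and 29, with further Day 15 samples at 1, 2, 4, 6 and 8 h. For the ECG, footnote i says: "On Days 1 and 15, ECGs will be collected before dosing and 4 hours (± 1 hour) after dosing".

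SAP 9.3.1 restricts the ppFEV1 MMRM to predose values at Day 15 and Week 4. SAP Appendix A (Table 12-1) assigns spirometry to visits by study day, with Day 15 covering (12, 22]. It takes the test closest to the target day and, among equally close tests, the latest.

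**The concern.** Item 5 is mandatory for afternoon visits, and its second branch removes the condition on which two other requirements depend. Once the morning dose has been taken at home, no test or sample at that visit can precede it.

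Two things are at stake. The ppFEV1 model uses only Day 15 and Day 29, in a part with 9 planned subjects on the triple combination and 3 on placebo, and SAP 9.1 does not impute missing post-baseline values. For PK, Day 15 is the only multi-sample profile after Day 1 in Part D, and on Days 8 and 29 the predose sample is the only one.

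There is also a separate ambiguity that needs no home dose. Every routine Day 15 visit has a predose and a 5 h postdose spirometry test on the same study day, and Appendix A does not distinguish them.

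**Working it through.** **1. Which visits are exposed.** Scheduled visits with dosing are Days 1, 8, 15 and 29. Day 1 is the first dose and is given in clinic, so the branch can apply only to Days 8, 15 and 29.

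**2. Can a predose value survive a home dose?** Inputs: the 6 h threshold (9.6.2 item 5), the ± 2 h dosing allowance (9.6.2 item 2) and the Part D predose PK window of 60 minutes before dosing (Table 11-1). Let d be how late (+) or early (−) the home dose is. Time from the home dose to the would-be clinic dose exceeds 6 − d:

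- d = −2 h: more than 8 h
- d = 0: more than 6 h
- d = +2 h: more than 4 h

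The predose window is −1 to 0 h, so none qualifies. With the protocol's 08:00 example, the branch begins when the clinic dose would fall after 08:00 + 6 h = 14:00.

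**3. Day 15 postdose items.** The last in-window time is the nominal time plus the allowance (PK + 0.25 h; ECG and spirometry + 1 h):

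| Item | Last in-window time after dose |
|---|---|
| PK 1 h | 1.25 h |
| PK 2 h | 2.25 h |
| PK 4 h | 4.25 h |
| ECG 4 h | 5 h |
| Spirometry 5 h | 6 h |
| PK 6 h | 6.25 h |
| PK 8 h | 8.25 h |

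The documents give no arrival times. Assume that the subject arrives a hours before the would-be clinic dose, with a between 0 and 2. First contact is then more than 6 − d − a hours after the home dose. For a home dose on schedule (d = 0):

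- a = 2: more than 4 h. The 1 and 2 h PK samples are past their windows, and the 4 h sample too if contact is after 4.25 h.
- a = 1: more than 5 h. The 1, 2 and 4 h PK samples and the 4 h ECG are past.
- a = 0: more than 6 h. As for a = 1, plus the 5 h spirometry.

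A home dose 2 h late with a = 2 gives more than 2 h, and then only the 1 h sample is certainly past. No single count is claimed. Late PK samples are protocol deviations under Table 11-1 and are not necessarily discarded.

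**4. Size in the ppFEV1 model.** Planned values are 9 × 2 = 18 on active treatment and 3 × 2 = 6 on placebo. One value not recovered is 1/18 = 5.6% or 1/6 = 16.7% of its arm. These are sizes per event, not risks.

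**5. Can Day 15 be recovered?** SAP 9.1 and Appendix A admit unscheduled tests to the visit windows, so a predose test on another morning in (12, 22] could serve. If that test is on Day 16, it is 1 day from target and the test after the home dose is 0 days from target. The closest-to-target rule alone would prefer the latter. Recovery therefore relies on the predose condition in SAP 9.3.1 being applied first.

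**6. The routine Day 15 visit.** The predose and 5 h tests are both 0 days from target. The tie goes to the later one, the 5 h postdose test. SAP 9.3.1 specifies predose. Appendix A gives the ECG nominal Day 15 predose and postdose entries but has none for spirometry.

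**7. Why Day 15 needs a tighter booking rule than Days 8 and 29.** If the clinic dose is D hours after the usual time, the 8 h PK sample falls at D + 8 h, while the usual evening IVA dose is at 12 h. D over 4 h puts the sample after that dose. At D = 6 h the sample falls at 14 h, which is 22:00 on the 08:00/20:00 example and the end of the ± 2 h allowance. Days 8 and 29 have only a predose sample, so a clinic dose within 6 h is enough there.

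**The case against.** The best reply is that compliant booking already avoids the branch. Protocol 11.7.5 makes the same-time rule a requirement, Day 1 is dosed in clinic with a morning dose, and a visit more than 6 h later is hard to reconcile with that. The 8 h Day 15 schedule points the same way. Home dosing is also the right fallback. The missed-dose rule skips a dose after 6 h, and a sample obtained by withholding longer would follow an abnormally long interval and would not be an ordinary trough.

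Much of this stands. It makes the event unlikely and supports keeping home dosing as a contingency. It does not remove the conflict, because item 5 expressly provides for afternoon visits and exempts none. The other possible rescues also fail. In footnote a, assessments due before and after dosing "will only be collected once if study drug is not administered on the day of the visit", which does not describe a day with a home dose. The flexibility over sampling times in Protocol 11.3.1 cannot restore a predose value.

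A reader might infer that item 5 contradicts item 4. It reads better as a specific exception to a general rule. A reader might also infer that an affected subject drops out of the MMRM. That is not supported either: a Day 15 value may be recovered, and the subject's other visit still contributes to the model.

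**Conclusion.** The point holds and is minor. Following item 5 as written at a late Day 8, 15 or 29 visit forfeits the predose spirometry and the 0 h PK sample and, on Day 15, at least the earliest postdose PK sample under the arrival assumption above. Each unrecovered Day 15 or Day 29 ppFEV1 value costs the shares shown in step 4. A lost Day 8 test does not enter the model.

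A reader might infer a material threat to the Part D efficacy result. The documents do not support that. They give no frequency for such visits, spirometry as efficacy is a secondary endpoint, Day 1 is unaffected, and visits dosed in clinic within 6 h keep their predose set. No placebo PK loss is claimed, since placebo samples are not routinely analyzed. Nor do the documents show that postdose values will be analyzed as predose. SAP 9.3.1 probably governs the model, but the literal Appendix A rule conflicts with it at every routine Day 15 visit.

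**What to change.** In Protocol 9.6.2 item 5, add three statements:

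- Day 8 and Day 29 visits are booked so that the morning dose is given in clinic within 6 h of the usual time, after the predose assessments.
- The Day 15 visit starts at the usual morning dose time, with the dose following the predose work.
- A visit that cannot meet this is first moved within the ± 1 day window. Home dosing remains only as a contingency.

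In SAP Appendix A, give spirometry separate Day 15 predose and postdose entries, as the ECG has. State that the Day 15 and Day 29 analysis values are the predose tests. List any spirometry taken after that day's dose, including a home dose, with its time since dose, and do not use it as the predose value.

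The cost is a short protocol addition, a short SAP clarification and slightly less appointment flexibility for about 12 subjects. No visit or procedure is added. Because home dosing stays available, an occasional loss remains possible.

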### **Missed Doses**

If a subject misses a dose and recalls the missed dose within 6 hours, the subject should take his/her dose with food. If more than 6 hours have elapsed after his/her usual dosing time, the

subject should skip that dose and resume his/her normal schedule for the following dose. For example:

- If the morning dose of study drug should have been taken at approximately 08:00, and the subject remembers at 12:00 that he/she forgot to take his/her dose, he/she should take the dose with food as soon as possible.
- If the morning dose of study drug should have been taken at approximately 08:00, and more than 6 hours have elapsed beyond the scheduled dosing time (i.e., the time is past 14:00), the subject would resume dosing with the evening dose at approximately 20:00.

## 9.7 Dose Escalation Criteria

### 9.7.1 Parts A, B, and C

The decision to initiate successive cohorts and dose selection will be based on safety and tolerability data from preceding dose group(s) and available PK data from a minimum of 6 subjects (to ensure 4 subjects receiving active drug) in the preceding cohort. The investigator, Vertex medical monitor, and Vertex Global Patient Safety (GPS) physician will conduct a blinded evaluation of all safety data on an ongoing basis, and all Grade 3 or higher laboratory abnormalities or AEs (Toxicity Grading Scale for Healthy Adult and Adolescent Volunteers Enrolled in Preventive Vaccine Clinical Trials) will be evaluated to determine if dosing/dose escalation should be continued. A safety report, which includes available PK data and justification for selection of the dose, will be prepared by the investigator for the proposed dose escalation.

**Part A:** The planned dose escalation scheme for Part A is shown in [Table 9-1](#). Doses may be adjusted upward or downward based on safety, tolerability, and available PK data from preceding dose group(s). No dose increment will be expected to yield greater than a 3-fold increase (Cohorts A1 through A3) or a 2-fold increase (all other Part A cohorts) in exposure from the preceding dose level. Dose escalation will be stopped when the predefined stopping criteria is met (see [Section 9.8.1](#)).

Cohort A2 initiation will be based on safety data (through  $\geq 48$  hours postdose) from Cohort A1. Cohort A3 initiation and dose selection will be based on safety data (through  $\geq 48$  hours postdose) from Cohort A2 and PK data (through  $\geq 24$  hours postdose) from Cohort A1 (i.e., lagging PK). For all other Part A cohorts, initiation and dose selection will be based on safety data (through  $\geq 48$  hours postdose) and PK data (through  $\geq 24$  hours postdose) from the previous cohort.

If conducted, the dose(s) in Cohorts A7 or A8 may be a replicate of a dose evaluated in Cohorts A1 through A6 or may be increased above 90 mg, pending emerging safety, tolerability, and PK data from Cohorts A1 through A6.

**Part B:** Part B may be initiated while Part A is ongoing after review of safety, tolerability, and PK data. The starting daily dose (Cohort B1) will be at least 1 dose level below the highest Part A dose for which safety and tolerability results are supportive.

The decision to initiate successive cohorts and dose selection will be based on safety data through the Day 10 Visit and PK data as available through the Day 5 Visit from the previous cohort. Doses may be adjusted upward or downward based on safety, tolerability, and PK data from preceding dose group(s). No dose increment will be expected to yield greater than a 2-fold

increase in exposure from the preceding dose level. The highest daily dose of VX-121 in Part B will not exceed the highest Part A dose for which safety and tolerability results are supportive. Stopping rules are presented in Section 9.8.1.

**Part C:** Part C may be initiated while Parts A and B are ongoing after review of safety, tolerability, and PK data. The starting dose (Cohort C1) will be at least 1 dose level below the highest Part B dose for which safety and tolerability results are supportive.

The decision to initiate successive cohorts and dose selection will be based on safety data through the Day 14 Visit and PK data as available through the Day 7 Visit from the previous cohort. The highest dose of VX-121 in Part C will not exceed the highest Part B dose for which safety and tolerability results are supportive.

